**Table 4: Visit Windows (Days)**

Visit	Relative Target Day	Visit Window (Day)
Screening a	-28 - -1	-28 – -1
Baseline/Day 1 b	1	1
Week 1 (Day 8)	8	2 – 11
Week 2 (Day 15)	15	12 – 21
Week 4 (Day 29)	29	22 – 35
Week 6 (Day 43)	43	36 – 49

Week 8 (Day 57)	57	50 – EOT+20
Post Treatment Week 4	EOT+28	EOT+21 – EOT+69
Post Treatment Week 12	EOT+84	EOT+70 – EOT+146
Post Treatment Week 24	EOT+168	EOT+147 – $\geq$ EOT+210

a. Screening window may be extended to 42 days for extenuating circumstances with Sponsor approval.  
b. Day 1 assessment prior to dosing

### **6.7.5. Multiple Assessments**

If multiple assessments are obtained within a visit window for a subject, the value obtained closest to the target timepoint will be used. For any visit, no more than one value per subject will be included in an analysis. In the event of multiple observations that are equidistant from the target day (e.g., two observations on the same day or observations made in a similar time frame before and after target), the earliest value, based on date and time, will be selected.

Multiple efficacy assessments will follow the rules outlined in section 8.7.1.

## **6.8. Handling of Missing Data**

### **6.8.1. Missing Efficacy Endpoints**

Backward imputation will be employed for subjects that do not have a week 4 or week 12 post treatment samples. The imputation will use the nearest post-treatment value that was collected after the missing sample. Missing data that cannot be imputed will be treated as failure.

Forward imputation may be employed for failures as described in Table 5.

Sensitivity analyses will be carried out to evaluate the impact of missing efficacy data.

In the analysis involving the safety population any missing SVR12 that cannot be imputed according to the rules outlined in Table 5 will be considered a failure.

### **6.8.2. Missing Start and Stop Dates for Prior and Concomitant Medication**

Where the start date for a concomitant medication is missing, the medication will be assumed to have started prior to enrolment in the study. Where the stop date for a concomitant medication is missing, the medication will be assumed to be ongoing to the date of the subject's last assessment.

### **6.8.3. Missing Start and Stop Dates for Adverse Events**

Where the entire start date for an adverse event is missing, the adverse event will be assumed to be treatment emergent. In this case, if the duration of an adverse event is computed, the start date will be considered as the date associated with Day 1. If the month and year of an adverse event is

provided, then the start date will be considered as the later date between the first day of the month/year and the treatment start date.

Where the stop date for an adverse event is missing, the adverse event will be assumed to be ongoing to the date of the subject's last assessment.

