## 7.2. Routine Reporting

For the purposes of this study, all AEs (serious and non-serious) will be recorded in the eCRF from the time of informed consent until 4 weeks after the last dose of study drugs. All SAEs will be recorded from the time of informed consent until the end of the study.

During these periods, all AEs spontaneously reported by the subject, observed by the clinical staff, or elicited by general questioning will be recorded and reported in the eCRF.

Any AE which remains unresolved as of the last visit will require follow-up until the AE has been resolved, a reasonable explanation for its persistence found, or is deemed chronic or stable by the investigator. It is the investigator's responsibility to ensure subjects experiencing AEs receive appropriate follow-up, treatment where required, and that every action is well documented.

Classification of AEs will be performed by System Organ Class and Preferred Term using The Medical Dictionary for Regulatory Activities (MedDRA).

Electronic case report form procedures for AE and SAE reporting can be found in the eCRF completion guidelines. Paper SAE forms are to be used only if the Electronic Data Capture (EDC) system is unavailable.

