## 8.5. Safety Analyses

Study treatment exposure (such as treatment duration and total dose received) will be summarized with descriptive statistics.

Treatment-emergent AEs and graded laboratory abnormalities, defined as any new or worsening AE/laboratory parameter beginning on or after the first dose of study drugs through 4 weeks after the last dose, will be included in the analysis.

Incidence and frequency of subjects experiencing AEs, SAEs, AEs resulting in treatment discontinuation, and AEs resulting in study discontinuation will also be summarized. Adverse events will be coded using MedDRA. The incidence and frequency of subjects with treatment-emergent adverse events will be tabulated by primary SOC and PT. The tabulation of the number of subjects with treatment-emergent AEs will also be provided by grade and relationship to study drug.

Changes from baseline in laboratory tests and vital signs will be summarized. Laboratory abnormalities will be graded in accordance with the DAIDS severity scale where applicable. Shift tables for treatment-emergent laboratory abnormalities will be presented.

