## **9. SAFETY AND TOLERABILITY**

### **9.1. Overall Summary of Tolerability**

All adverse events will be coded according to the Medical Dictionary for Regulatory Activities (MedDRA) and will be summarized for the safety population. Only treatment-emergent adverse events (TEAE) will be summarized. Treatment emergent adverse events are those with start date/time within the treatment period, defined as the time from first study drug administration to 4 weeks post treatment. Events that occur after 4 weeks with relationship to study drug recorded as 'related' will also be considered as treatment emergent. If the AE onset date is missing or partial, the conventions described in Section **Error! Reference source not found.** will be used to determine if the event is treatment emergent.

Adverse event severity will be graded according to the Division of AIDS (DAIDS) Table for Grading the Severity of Adult and Pediatric Adverse Events, Version 2.1 dated July 2017.

An overall summary of adverse events will be presented and include tabulations (number and %, unless otherwise indicated) for the following:

- Subjects with at least one TEAE, overall and by worst grade
- Total number (number only) of TEAEs
- Deaths
- Subjects who discontinued study due to an AE
- Subjects who discontinued treatment due to an AE
- Subjects with a treatment related AE resulting in treatment discontinuation
- Subjects with a serious adverse event (SAE)
- Subjects with a treatment related SAE
- Subjects with a treatment related AE, overall and by worst grade
- All Adverse Events will be listed

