### **9.2.2. Missing and Partial AE Onset Dates**

Missing or partial AE start dates will be handled in accordance with section 6.8.3.

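### SAP 6.8.3 moves an adverse event recorded in a month before the first-dose month onto Day 1, so it is counted as treatment-emergent against its own recorded date

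*SAP*

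**What the plan says.** SAP 6.8.3 has two rules for onset dates.

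- No date at all: "Where the entire start date for an adverse event is missing, the adverse event will be assumed to be treatment emergent".
- Month and year known, day missing: "then the start date will be considered as the later date between the first day of the month/year and the treatment start date". There is no exception for a month earlier than that of first dose, and the stop date plays no part.

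The convention decides TEAE status. SAP 9.1 says that the conventions for missing or partial onset dates "will be used to determine if the event is treatment emergent". Its section reference is a broken field, but SAP 9.2.2 supplies the target: "Missing or partial AE start dates will be handled in accordance with section 6.8.3".

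The definitions agree on the starting point. SAP 9.1: "Treatment emergent adverse events are those with start date/time within the treatment period", a period "defined as the time from first study drug administration to 4 weeks post treatment". Protocol 8.5 counts new or worsening events "beginning on or after the first dose of study drugs through 4 weeks after the last dose".

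Collection starts earlier. Protocol 7.2: "all AEs (serious and non-serious) will be recorded in the eCRF from the time of informed consent until 4 weeks after the last dose". Protocol section 6 sets screening at 28 days, extendable to 42 with sponsor approval, and Table 2 schedules adverse event review at Screening and Baseline.

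**The concern.** Taking the later of two dates is a normal conservative choice when the timing is uncertain. Here it also applies where there is no uncertainty. If the site recorded a month that ended before the month of first dose, the event began before treatment whatever the missing day was. The rule replaces that information with Day 1. It can also give an imputed start later than a known stop date, if the event resolved before dosing.

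Safety and tolerability is a primary objective, and SAP 9.1 restricts the adverse event summaries to TEAEs. An event moved in this way enters the main tables by system organ class, preferred term and severity. The trial has one arm, so no control group carries the same misclassification for comparison.

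**Working it through.** The plan gives no figure to reproduce. The check applies the rule as written and then asks how often it would contradict the recorded month.

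**Step 1. The rule as a formula.** Imputed start = max(first day of recorded month, first-dose date). This is never earlier than first dose, so every event with month and year known and day missing is placed on or after Day 1.

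**Step 2. Example.** First dose 10 April 2023 (illustrative), with study day as in SAP 6.7.2. The corrected rule is the one given under the fix.

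| Recorded onset | SAP rule | Status | Corrected rule | Status |
|---|---|---|---|---|
| March 2023 | 10 April, Day 1 | TEAE | 1 March, Day -40 | not TEAE |
| April 2023 | 10 April, Day 1 | TEAE | 10 April, Day 1 (no stop date before dosing) | TEAE |
| May 2023 | 1 May, Day 22 | TEAE | 1 May, Day 22 | TEAE |

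Only the first row is contradicted by the recorded data. In the second the timing is truly ambiguous. In the third the month alone shows onset after first dose.

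**Step 3. Share of pre-dose partial dates in an earlier month.** Inputs: screening of 28 or 42 days (protocol section 6). Assumptions: onset is uniform over screening, and first dose is equally likely on each day d of a 30-day month. An onset k days before dosing lies in an earlier month when k ≥ d.

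- 28 days: the pairs (k, d) with k ≥ d number 1 + 2 + … + 28 = 406, out of 28 × 30 = 840. 406/840 = 0.483.
- 42 days: (1 + 2 + … + 30) + 12 × 30 = 465 + 360 = 825, out of 42 × 30 = 1260. 825/1260 = 0.655.

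Running every first-dose date in calendar year 2023 instead gives 0.477 and 0.650. Under the SAP rule 100% of these pre-dose events become TEAEs. With the month condition alone, 52% (28 days) or 35% (42 days) remain TEAEs, all of them in the first-dose month.

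**Step 4. Effect on the headline rate.** The documents give no number of affected subjects. For illustration, 3 subjects out of 280 is 3/280 = 1.1 percentage points, and only if none of the three has another TEAE.

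**The case against.** The best defence concerns reach, not logic.

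- An affected event must begin between consent and first dose, lack a day, fall in an earlier month, and stay partial after the data checks and site queries in protocol 10.2 and SAP 6.3. Symptoms before consent go to medical history (protocol 7.1). A reader might infer that such events are bound to arise. The documents show only that they can.
- A reader might take 48% to 65.5% as the share of adverse events misclassified. It is a share of pre-dose events with a missing day, a subset of unknown and probably very small size.
- A reader might infer that the TEAE rate is materially inflated. SAP 6.1 counts a subject once per category, so a moved event in someone who already has a TEAE leaves the overall subject rate unchanged. A screening event that worsens on treatment is treatment-emergent anyway under protocol 8.5.
- No decision depends on the total TEAE rate. The analysis is descriptive (SAP 8.1, 8.4), and the pausing rules in protocol 5.6.3 use confirmed ALT/AST elevations and events that the investigator considers related. Drug-related summaries should be little affected, since a pre-dose event is unlikely to be attributed to study drug. SAP 9.1 also lists all adverse events.
- The direction is conservative, like the rule for wholly missing dates.

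All of this limits the size, and it stands. It does not defend the rule. Conservative imputation settles what is unknown; here the recorded month settles the question and is overwritten. No other section of either document corrects it.

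**Conclusion.** The point holds as a wording error with a definite wrong result. Under SAP 6.8.3, an adverse event with a missing day and a recorded month before the first-dose month becomes a Day 1 TEAE, against SAP 9.1 and protocol 8.5. The rule needs no change for later months, and for the first-dose month it needs only a stop-date check.

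When the error occurs it can only add to TEAE counts. Its frequency cannot be derived from the documents and may be zero. The 48% and 65.5% rest on uniform onset and a random dosing day; the 1.1 points rest on an invented count of three subjects. Nothing supports a claim that the safety conclusions or SVR12 would change. The case for correcting it is that the error is certain whenever such a date is recorded, touches a primary objective, and is cheap to remove.

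**What to change.** Reword the partial-date rule in SAP 6.8.3 along these lines:

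1. If the recorded month and year equal those of first dose, use the treatment start date, unless a known stop date is before first dose. In that case the event is not treatment-emergent.
2. Otherwise use the first day of the recorded month. Earlier months then stay pre-treatment and later months are handled as now.

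Point the broken cross-reference in SAP 9.1 to section 6.8.3.

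The cost is a sentence or two in the SAP and a short change to the derivation code. No data collection changes. SAP section 2 allows the plan to evolve until it is finalised before database lock. One side effect is that the first of an earlier month may precede consent; this affects a computed duration but not TEAE status.

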## 7. STUDY POPULATION

### 7.1. Subjects Disposition

The following will be tabulated (number and percentage) for the screened population:

- Received study drug.
- Did not receive study drug.
- Completed treatment.
- Discontinued treatment, overall and by reason.
- Completed assessment through Post Treatment Week 24.
- Did not complete assessment through Post Treatment Week 24, overall and by reason.

The following will also be tabulated (number and percentage) for the screened population:

- Subjects screened and treated in each country and investigator site.
- Subjects included and excluded (with reason) for each analysis population.

### 7.2. Screen Failures

The numbers and proportions of subjects who screened but were not treated will be presented as:

- Screen failures
- Subjects who do not have indication of failing to meet I/E criteria but were not treated.

Screen failure reasons will also be tabulated. A subject may have more than one reason for screen failure and all reasons for a subject will be counted, i.e., the sum of subjects across screen failure reasons may exceed the total number of screen failures.

### 7.3. Protocol Deviations

A final identification and classification of important protocol deviations will be made prior to the freezing of the database and will be documented. The number and percentage of subjects with important protocol deviations and the total number of important protocol deviations by reason (e.g., nonadherence to study drug, violation of select inclusion/exclusion criteria) will be summarized for the enrolled population. A by-subject listing will be provided for those participants with important protocol deviations.

### 7.4. Demographic and Baseline Characteristics

Descriptive summaries of demographic and baseline characteristics will be presented on the enrolled, safety, efficacy evaluable per-protocol, pill compliant per-protocol and pk and pill compliant per-protocol populations.

Demographic variables and baseline characteristics to be summarized may include:

- Age
- Sex

- Race
- Ethnicity
- Region
- Weight
- BMI
- HCV genotype (HCV GT1, GT2, GT3, GT4, GT5, GT6 or GT7)
- Cirrhotic status (non-cirrhotic and compensated cirrhosis)
- Fibrosis stage (F0, F1, F2, F3, and F4)
- HCV RNA quantification (e.g., baseline viral load)
- Prior HCV treatment

## **7.5. Medical History and Medical Conditions Present at Entry**

Complete medical history will be obtained at screening. Medical history records will be coded, using the current version of Medical Dictionary for Regulatory Activities (MedDRA), and summarized by system organ class and preferred term using the safety population.

## **7.6. Prior Medication History and Medications Present at Entry**

Medication will be coded to ATC level 4 using the most recent version of the World Health Organization Drug Dictionary (WHODRUG). Prior medications will be summarized descriptively for the safety population. Prior medications that have been stopped prior to date of first study drug dose will be summarized separately from medications that were started and continued into the study drug treatment period.

A summary of prior medications with indication of HCV will also be provided.

### **7.6.1. Non-Diagnosis Related Prior Medication History**

All medical history data will be listed.

### **7.6.2. Prior Diagnosis Related Medication History**

Enrolled subjects will be DAA treatment naïve, however prior exposure to (peg)interferon with or without ribavirin will be collected and summarized.

## **7.7. Baseline Physical Examination**

A complete physical examination will be performed by a medically qualified individual at baseline. The complete physical examination will include a review of the following: head and neck, ears/nose/throat, lymph nodes, heart, lungs, abdomen, musculoskeletal, neurological, skin, and general appearance.

All clinically significant findings will be recorded as medical history.

## **7.8. Baseline Vital Signs**

Vital sign measurements (body temperature, pulse rate and blood pressure) will be measured at baseline after subjects have had at least 3 minutes of rest. Body weight will be recorded, and BMI will be calculated.

## **7.9. Baseline Laboratory Data**

Laboratory evaluations at baseline will include:

- Serologies for HCV (anti-HCV antibody), HBV (HBsAg), and HIV
- HbA1c
- Hematology: hematocrit, hemoglobin, platelet count, red blood cell count, white blood cell count with differential (absolute) including lymphocytes, monocytes, neutrophils, eosinophils, basophils, reticulocyte count, and mean corpuscular volume
- Coagulation: INR, prothrombin time
- Chemistry: ALT, AST, albumin, alkaline phosphatase, creatine kinase, creatinine, blood urea nitrogen or urea, eGFR calculation (MDRD), total bilirubin (reflex to direct bilirubin), glucose, amylase, lipase, potassium, sodium, bicarbonate, or total carbon dioxide
- Urinalysis: appearance, blood, color, glucose, leukocyte esterase, pH, protein, urobilinogen. Reflex to microscopic urinalysis if dipstick result is abnormal
- Serum or urine pregnancy test on females of childbearing potential

## **7.10. Baseline Primary and Secondary Efficacy Evaluations**

Baseline HCV RNA will be quantified, and will be categorized based on greater than or equal to the median as the high-low high cut-off point.

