#### **8.4.2. Secondary Analyses**

Secondary analyses will include:

- The proportion of subjects in the PP population(s) experiencing virologic failure (on treatment or post-treatment relapse) by 12 weeks post treatment), estimated and presented with 95% CIs.
- The proportion of subjects in the PP population(s) achieving SVR24, analyzed using the same method as for SVR12.

Additional exploratory analyses will be performed and may include (but not be limited to) the following:

- The proportion of subjects in the PP population(s) achieving SVR12 by baseline NS5A and NS5B RAVs (yes/no), estimated and presented with 95% CIs.
- Emergence of NS5A and NS5B RAVs in the PP population(s), tabulated with proportions and CIs in subjects who experience virologic failure
- Assessment of response (e.g., SVR12 rates) by demographics and/or baseline characteristics including prior HCV treatment, baseline viral load, etc.

- HCV RNA change from baseline over time
- Exposure-response relationships

Additional details will be provided in the SAP.

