### **8.4. Statement of the Null and Alternate Hypotheses**

No statistical test is planned.

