### **8.5. Subgroup Analyses**

Subgroup analysis will be performed according to the following baseline characteristics:

- HCV genotype (HCV GT1, GT2, GT3, GT4, GT5, GT6 or GT7)
- Cirrhotic status (non-cirrhotic, compensated cirrhosis)
- Fibrosis stage (F0, F1, F2, F3, or F4)
- Baseline resistance-associated variants
- Baseline viral load

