## 8.9. Analysis of Exploratory Efficacy Endpoints

Exploratory efficacy analyses for all populations include:

- Proportion of subjects with SVR12 by HCV genotype and presence of baseline NS5A and NS5B RAVs.
- Proportion of subjects with SVR24 by HCV genotype and presence of baseline NS5A and NS5B RAVs.
- Proportion of subjects with SVR4 by HCV genotype and presence of baseline NS5A and NS5B RAVs.
- The proportion of subjects achieving SVR24, analyzed using the same method as for SVR12.
- Proportion of emergence of NS5A and NS5B RAVs in subjects who experience virologic failure. Results will also be summarized by genotype.
- Proportion of baseline NS5A and NS5B RAVs in subjects who experience virologic failure. Results will also be summarized by genotype.
- Prevalence of specific baseline and treatment-emergent NS5A and NS5B RASs by genotype and by virologic failure at SVR12
- SVR12 will be estimated and presented with 95% CIs by demographics and/or baseline characteristics including prior HCV treatment and baseline viral load (baseline viral load will be categorized using the median as a low-high cut-off point).
- HCV RNA IU/ml log10 value will be tabulated by HCV genotype and the average change from baseline over time will be plotted.
- Qualitative HCV RNA results will be tabulated by HCV genotype over time
- Exposure-response relationships will be explored by scatter plots of drug exposure versus change in HCV RNA IU/ml log10 value.

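### The only planned analysis of SVR12 by baseline HCV RNA is a median split; adding an estimate on continuous log10 HCV RNA would recover information when only about 13 failures are expected.

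*SAP*

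**What the plan says.** SAP 7.10 states that baseline HCV RNA "will be categorized based on greater than or equal to the median as the high-low high cut-off point". SAP 8.9, under the lead-in "Exploratory efficacy analyses for all populations include", plans SVR12 with 95% CIs by baseline characteristics and repeats the rule: "baseline viral load will be categorized using the median as a low-high cut-off point". SAP 8.5 lists "Baseline viral load" as a subgroup factor without a cut-off. Protocol 8.4.2 includes among its additional exploratory analyses "Assessment of response (e.g., SVR12 rates) by demographics and/or baseline characteristics including prior HCV treatment, baseline viral load, etc", again without a cut-off or model.

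HCV RNA appears in two other places. SAP 7.4 lists it among the baseline characteristics to be summarised, and SAP 8.9 says that the log10 "value will be tabulated by HCV genotype and the average change from baseline over time will be plotted". Neither relates baseline load to SVR12 or failure. On inference, SAP 8.4 says: "No statistical test is planned".

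No IU/mL value is given for the cut-off, and the population that supplies the median is not named.

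**The concern.** SVR12 in baseline subgroups is an exploratory endpoint in both documents, and baseline viral load is one of the named factors. The study is meant to explore an 8-week course and to inform later studies, so whether failures cluster at high viral load is a natural question.

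A split at the median treats every value above it alike. Entry requires at least 1,000 IU/mL with no upper limit (Protocol 4.2), so a subject just above the median is pooled with the highest load in the study. If risk rises steadily with viral load, the split blurs the gradient; if it is confined to the top of the range, the split dilutes it. With few failures expected, little information is available to begin with, and the planned method uses only part of it.

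**Working it through.** **The plan's own figures.** The documents give no figure for the viral-load analysis. The sample size on which it rests reproduces: 0.95 × 280 = 266 and 0.95 × 75 = 71.25, taken as 71 (SAP 4.3.1). The bounds in SAP Table 3 also reproduce as one-sided 95% Wilson limits; for example, 240/266 gives 86.8% (table: 87%) and 64/71 gives 82.8% (table: 83%).

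**Expected failures.** SAP 4.3.1 discusses an observed SVR rate around 95%. Taking 95% as an assumption, 266 × 0.05 = 13.3 failures.

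**Information kept by a median split, small linear effect.** This is the squared correlation between the covariate X, centred at its median, and its sign: (E|X|)² / Var(X).
- Normal X: (√(2/π))² / 1 = 2/π = 0.637. The loss is 36%, and 266 subjects act like 266 × 0.637 = 169.
- Uniform X on (−1, 1): (1/2)² / (1/3) = 0.75. The loss is 25%.

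**Few failures and larger effects.** Simulation with N = 266, normal log10 HCV RNA, a logistic model for failure and 4,000 trials per setting. The failure rates and odds ratios are assumptions. Score statistics were computed for the continuous value and for the median split. The information loss is 1 minus the squared ratio of their mean z values.

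| Odds ratio per SD | Loss, 2% failures | Loss, 5% failures | Loss, 10% failures |
|---|---|---|---|
| 1.5 | 37% | 39% | 37% |
| 2 | 45% | 42% | 39% |
| 3 | 53% | 49% | 44% |

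The proportion of trials in which |z| exceeds 1.96 serves here only as a gauge of sensitivity, since no test is planned. At 5% failures it is, continuous against split:
- odds ratio 1.5 per SD: 32% against 20%
- odds ratio 2 per SD: 65% against 43%
- odds ratio 3 per SD: 94% against 77%

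To read these per log10, note that the odds ratio per SD equals the odds ratio per log10 raised to the power SD. With an assumed SD of 0.6, an odds ratio of 2 per log10 is 2^0.6 = 1.52 per SD; with an SD of 0.8, an odds ratio of 3 per log10 is 3^0.8 = 2.41 per SD.

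**How precise the continuous estimate would be.** Near the null, the standard error of the log odds ratio per SD is about 1/√(266 × 0.05 × 0.95) = 1/√12.6 = 0.28. With an SD of 0.8 this is 0.28/0.8 = 0.35 per log10, so the 95% limits are the estimate divided and multiplied by about exp(1.96 × 0.35) = 2.0. With an SD of 0.6 the standard error is 0.28/0.6 = 0.47 and the factor is exp(1.96 × 0.47) = 2.5.

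**If the median were recomputed in each population.** Simulated with an SD of 0.8 and 14 of 280 subjects dropped at random, the median moves by no more than 0.03 log10 in 95% of runs. About 1.4 subjects change group on average (95th percentile 4).

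**The case against.** The strongest reply is that this is one exploratory, descriptive table. No test is planned, so power does not measure anything the trial will do. The median rule is prespecified and uses baseline data only, which leaves no room for choosing a cut-point after seeing outcomes. Protocol 1.1 names genotype 3, prior DAA failure and cirrhosis as harder to treat, and does not name viral load. Baseline HCV RNA will be summarised, by default with quartiles and range (SAP 6.1), and listed by subject (Protocol 8.3), so a reader could see where about 13 failures lie. With so few failures, a continuous analysis is also weak for moderate effects.

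Most of this stands, and it limits the importance of the point. It does not remove it: a listing is not an estimate, and a weak data set is a reason to keep the information it has. Protocol 8.4.2 leaves its exploratory list open, and an odds ratio with a CI is estimation, so the addition fits the plan.

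A reader might also infer that the cut-off shifts from one population to the next, because SAP 8.9 applies to all populations. The SAP does not say so. It refers to a single median and leaves its source unnamed; even if the median were recomputed, only one or two subjects would typically switch. Nor do the documents support a fixed loss of one third: that figure needs a normal covariate and a small linear effect.

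**Conclusion.** The point holds as a cheap improvement to an exploratory analysis. A high/low split at the sample median is the only specified link between baseline HCV RNA and SVR12. It discards roughly 25% to 50% of the information on any association: 25% for a uniform covariate, 36% for a normal covariate with a small linear effect, and about half for a strong effect with few failures. It cannot show a gradient or isolate a risk at the highest loads. The covariate shape, SD, effect sizes and 95% SVR are assumptions; the documents give no figures for this analysis.

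It would be wrong to infer that the SVR12 result is affected. The primary and secondary endpoints, the lead-in rule and the sample size are untouched. The unnamed source of the median is a missing detail of little numerical consequence.

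**What to change.** In SAP 8.9, keep the median-split table and add a Firth-penalised logistic regression of SVR12 failure on continuous log10 baseline HCV RNA. Report the odds ratio per log10 with a 95% CI and no p-value, and state that the estimate is imprecise because failures are few. The penalised form is suggested because about 13 events can give biased or unstable ordinary estimates. A single linear term will show a gradient and gives extreme values their weight. It will not separate a steady gradient from a threshold, and 13 failures could hardly support more.

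As a minor clarification in SAP 7.10, state that one median, for example that of all treated subjects, is used in every population. This settles the programming; it does not make the cut-off more portable to other studies, because it remains a sample median.

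The cost is a few lines of SAP text and one extra exploratory table with a wide interval. No new data are needed.
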